10.3.1.5. Missing Data Imputation Methods

10.3.1.5.1. Non-responder Imputation for Clinical Response

Summaries for all categorical efficacy and health outcomes variables will include a summary that uses a nonresponder imputation (NRI) approach. In this approach, participants will be considered a non-responder if they do not meet the clinical response criteria at any specified analysis time point. Participants without at least 1 observation on study treatment will also be defined as a non-responder for the NRI analysis. All participants who discontinue the study treatment will be defined as non-responders for the NRI analysis for categorical variables, such as JIA ACR 30/50/70/90/100, from the time of discontinuation and onward.

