- intercurrent event strategy:** The analysis population will be based on patients who have had the chance to complete the visits. In the estimand framework, for primary variable, the composite estimand strategy will be applied and non-responder imputation will be used to support this strategy. Patients will be considered non-responders for the nonresponder imputation (NRI) analysis if they do not meet the clinical response criteria or have missing clinical response data at the analysis time point of interest. All nonresponders at Week 16 (Visit 8), as well as all patients who discontinue study treatment at any time prior to Week 16 for any reason, will be defined as non-responders for the NRI analysis at Week 16.

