6.3. Handling of Dropouts or Missing Data

6.3.1. Non-Responder Imputation for Clinical Response

The NRI method may be used to address missingness when the estimand of interest uses the composite strategy for handling intercurrent events.

Analysis of categorical efficacy and health outcome variables will be assessed using a NRI method. Patients will be considered non-responders for the NRI analysis if they do not meet the clinical response criteria or have missing clinical response data at the analysis time point of interest. All nonresponders at Week 16 (Visit 8), as well as all patients who discontinue study treatment at any time prior to Week 16 for any reason, will be defined as non-responders for the

NRI analysis at Week 16. For the OLE Period Population, all non-responders at Week 104 (Visit 29), as well as patients who discontinue the originally assigned study treatment at any time prior to Week 104 for any reason, will be defined as non-responders for the NRI analysis at Week 104. For the Switcher population, all non-responders at Week 104 (Visit 29), as well as patients who discontinue ixekizumab after the switch at any time prior to Week 104 for any reason, will be defined as non-responders for the Week 104 analysis.

The NRI will be applied at any time point specified for analysis.

6.3.2. *Last Observation Carried Forward*

When last observation carried forward (LOCF) is applied, the last nonmissing postbaseline observation on or prior to the missed visit within the same period will be carried forward to subsequent time points for evaluation. Patients without at least 1 postbaseline observation will not be included for evaluation. This method will be used to handle missing data for individual components of a composite endpoint, such as JIA ACR or Disease Flare. Further details are described in [Appendix 1](#) and [Appendix 2](#).

6.3.3. *Modified Baseline Observation Carried Forward*

A complete guideline on statistical principles for clinical trials such as impact on trial design, conduct, and analysis, and documenting estimands and sensitivity analysis can be found in the *ICH E9 Statistical Principles for Clinical Trials* and the *addendum (R1)* (EMA 2020).

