If any patients missed a visit or discontinued study treatment due to the restriction of coronavirus disease 2019 (COVID-19) in the OLT period for the OLT period population, a multiple imputation (MI) method will be used to impute missing data for each component of JIA ACR30, and JIA ACR30 up to Week 16 will be derived using the MI-imputed components. In the MI analyses, missing data will be imputed to estimate what the observations would have been if the patient had not missed a visit or discontinued due to COVID-19. Specifically, MI is the partial imputation of nonmonotone missing data using Markov chain Monte Carlo method with the simple imputation model, followed by a sequential regression. All other missing JIA ACR30 up to Week 16 due to other reasons will be imputed with NRI.

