The posterior mean, variance, and 95% credible interval will be summarized from this posterior distribution. The following will be provided:

- The posterior mean,

$$\mu_p = \frac{a + k}{a + b + n}$$

- The posterior standard deviation,

$$\sigma_p = \sqrt{\frac{(a + k)(b + n - k)}{(a + b + n)^2(a + b + n + 1)}}$$

- 95% credible interval, which will include the 2.5th and 97.5th percentiles of the posterior distribution

The beta posterior probability of the response rate exceeding 0.5 is given by:

$$\begin{aligned} P(p > 0.5|k) &= \int_{0.5}^1 \frac{1}{B(a + k, b + n - k)} p^{a+k-1} (1 - p)^{b+n-k-1} dp \\ &= \int_{0.5}^1 \frac{1}{B\left(\frac{1}{2} + k, \frac{1}{2} + n - k\right)} p^{k-1/2} (1 - p)^{n-k-1/2} dp \end{aligned}$$

where:

$$B(\alpha, \beta) = \int_0^1 t^{\alpha-1} (1 - t)^{\beta-1} dt$$

$$\alpha > 0, \beta > 0$$

is the beta function.

The following example and SAS® code illustrate how the posterior probability is obtained.

```
%macro bayesian_algo (p_0=, a=, b=, k=, n=);
  data bayesian;
    p=&k/&n;
    a_post=&a+&k;
```

```
b_post=&b+&n-&k;
k=&k;
n=&n;
h_0=&k/&n;
h_1=1-&k/&n;
x1=probbeta(h_0,a_post,b_post);
x2=1-probbeta(h_1,a_post,b_post);
postProb=1-probbeta(&p_0,a_post,b_post);

run;
%mend bayesian_algo;

%bayesian_algo(p_0=0.5,a=0.5,b=0.5,k=35,n=80);
```

Table RHCG.6.5. Description and Derivation of Primary Efficacy Endpoint

Measure	Description	Variable	Derivation/Comment	Imputation Approach if with Missing Components
JIA ACR30 Responder Index	Juvenile Idiopathic Arthritis American College of Rheumatology, JIA ACR, is comprised of 6 variables: active joint count, limitation of motion joint count, physician global assessment, patient/parent global assessment, Childhood Health Assessment Questionnaire (CHAQ), and acute-phase reactant level (ESR). A JIA ACR30 response is defined as at least 30% improvement from baseline in at least 3 of any 6 variables in the core set, with no more than 1 of the remaining variables worsening by more than 30% (Giannini et al. 1997).	Proportion of patients with Juvenile Idiopathic Arthritis American College of Rheumatology (JIA ACR) 30 at Week 16, nonresponder imputation (NRI)	See Section 6.9.1 and Appendix 1	See Appendix 1

Abbreviations: ACR = American College of Rheumatology; ESR = erythrocyte sedimentation rate; JIA = Juvenile Idiopathic Arthritis; NRI = nonresponder imputation.

Table RHCG.6.6. Description of Analysis Period and Analysis Method of Primary Efficacy Endpoint

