Count how many variables have more than 30% worsening; if the worsening count is 2 or more, conclude that the patient is a nonresponder. If the worsening count is 1 or less, proceed to Step 2.

Step 2: Improvement (count):

Check $\geq 30\%$ improvement. Specifically, check if percent change from baseline is less than or equal to -30% , i.e.,

$$\text{If } (\text{parameter} \leq -30\%) = 1, \text{ else } 0$$

Count how many variables have at least 30% improvement; if the count is 3 or more, conclude that the patient is a responder; if count is 2 or less, conclude that the patient is a nonresponder.

Note:

Scenario 1: If no variable is missing, proceed as described in Step 1 and/or Step 2, whichever applies.

Scenario 2: If there are variables missing at post-baseline, apply last observation carried forward (LOCF) first at component level, then back to Scenario 1 (LOCF cannot be applied across study periods, and the patient needs to have at least 1 post-baseline visit to apply LOCF. The baseline value cannot be carried forward).

Note for ESR : If the *esr* at a particular visit is missing, then the last observation is carried forward for the visit. However, for the LOCF visit, if the elevation is attributable to a medical condition other than the study condition as well, then the *esr* value at the current visit is treated as missing.

Scenario 3: If there are variables missing at baseline, use nonmissing components as the core sets, then back to Scenario 1. Unless specified otherwise, if there are variables with baseline value = 0, all postbaseline percent improvement is not calculable; hence, consider these variables as missing and use nonmissing components as core sets, then back to Scenario 1.

Note: for Scenario 3:

- If 1 component is missing, the remaining 5 components will be used as core set. If 3 out of 5 components are improving and no more than 1 out of 5 is worsening, the patient will be considered as a responder.
- If 2 components are missing, the remaining 4 components will be used as core set. If 3 out of 4 components are improving and no more than 1 out of 4 is worsening, the patient will be considered as a responder.
- If 3 components are missing, the remaining 3 components will be used as core set. If all 3 components are improving, the patient will be considered as a responder.
- If more than 3 components are missing, there will not be sufficient information; thus, the patient will be considered as a nonresponder.

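### For an on-treatment ixekizumab participant who misses the whole Week 16 visit, the SAP's missing-response rule gives non-response but its component LOCF rule can give response, and no text says which governs the primary endpoint

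*SAP*

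**What the plan says.** **Response-level rule.** SAP 4.1 adopts a composite strategy supported by non-responder imputation (NRI). Participants are non-responders "if they do not meet the clinical response criteria or have missing clinical response data at the analysis time point of interest". Discontinuers are added by a separate clause, "as well as all patients who discontinue study treatment at any time prior to Week 16 for any reason". SAP 6.3.1 repeats both clauses. The missing-data clause is therefore not confined to participants who stopped treatment.

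**Component-level rule.** Under SAP 6.3.2, "the last nonmissing postbaseline observation on or prior to the missed visit within the same period will be carried forward to subsequent time points", and the section assigns this method to the components of JIA ACR. Appendix 1 Scenario 2 reads: "If there are variables missing at post-baseline, apply last observation carried forward (LOCF) first at component level". The participant is then scored as if nothing were missing. The only conditions are at least one post-baseline visit, no carrying across study periods and no carrying of baseline. The cut-off of more than three missing components belongs to Scenario 3, which deals with components missing or zero at baseline.

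**Texts that might settle the order.**
- SAP Table RHCG.6.5 names NRI for the response and Appendix 1 for missing components in one row, without an order for a wholly missed visit.
- SAP 6.3.4 sends visits missed because of COVID-19 restrictions to multiple imputation of the components. For the rest it says: "All other missing JIA ACR30 up to Week 16 due to other reasons will be imputed with NRI". SAP 6.9.5 uses this method only as a sensitivity analysis.
- Protocol 10.3.1.5.1 has a general rule that participants not meeting the criteria at the time point are non-responders. It adds: "Participants without at least 1 observation on study treatment will also be defined as a non-responder for the NRI analysis". It also covers discontinuers, but does not expressly address an on-treatment missed visit.

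**The concern.** The SAP can score the same participant two ways on the primary endpoint. If LOCF runs first, all six components are filled, the response is no longer missing and the NRI clause is never triggered. A response at Week 12 is then credited as a response at Week 16, although SAP 4.1 counts absent Week 16 data as non-response. If NRI runs first, the participant is a non-responder. Two programmers working from different sections could report different primary results near the cut-off. In an open-label study the choice should be fixed before the result is known.

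**Working it through.** **Who is affected.** The OLT period ends just before the Week 16 injection (SAP 6.1.2.1), so Weeks 2 to 12 and the pre-dose Week 16 assessment fall in one period. The Schedule of Activities collects all six components at each of these visits, so all six can be filled from Week 12. Participants who discontinue treatment before Week 16 are non-responders by their own clause. Participants with no post-baseline value have nothing to carry. The conflict is limited to on-treatment participants with an earlier post-baseline visit.

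**Illustration (invented values, baseline to Week 12; Week 16 wholly missed).** Active joints 10 to 4 (-60%), limited joints 8 to 4 (-50%), physician global 6 to 2 (-67%), parent global 50 to 25 (-50%), CHAQ 1.5 to 1.0 (-33%), ESR 40 to 22 (-45%). Scenario 2 counts six components improved by at least 30% and none worsened: a responder. SAP 4.1 read directly gives a non-responder.

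**The plan's own figures.** The inputs are n = 80 (SAP 5.2), prior Beta(0.5, 0.5), and success if P(p > 0.5) is at least 0.80 (Protocol 10.3.3.1, SAP 6.9.1). The posterior is Beta(0.5 + k, 0.5 + 80 - k).
- k = 43: P(p > 0.5) = 0.7487, negative.
- k = 44: P(p > 0.5) = 0.8144, positive.

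This reproduces the SAP 6.15.1 threshold of fewer than 37 non-responders (80 - 44 = 36). P(Bin(80, p) >= 44) is 84.8% at p = 0.60 (stated: above 80%) and 0.02% at p = 0.35 (stated: below 1%).

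**The two readings.** Let m participants miss the whole Week 16 visit (m is assumed) and let q be the response probability from carried-forward values.
- NRI: P(Bin(80 - m, p) >= 44).
- LOCF: P(Bin(80 - m, p) + Bin(m, q) >= 44).
- For m = 1 the gap is q × P(Bin(79, p) = 43). At p = 0.55 this is 0.55 × 0.0894 = 0.0492.

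| True rate p | LOCF, q = p | NRI, m = 1 | Gap, m = 1 (points) | Gap for q = p - 0.10 to p + 0.10, m = 1 | NRI, m = 2 |
|---|---|---|---|---|---|
| 50% | 21.7% | 18.4% | 3.3 | 2.6 to 4.0 | 15.4% |
| 55% | 54.6% | 49.7% | 4.9 | 4.0 to 5.8 | 44.7% |
| 60% | 84.8% | 81.5% | 3.3 | 2.7 to 3.8 | 77.8% |

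**False-positive rate.** At p = 0.35, with every missed visit carried forward as a response, P(Bin(80 - m, 0.35) >= 44 - m) is 0.03% for m = 1 and 0.05% for m = 2.

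These figures leave out the interim futility stop. With no missed visits, including it changes the success probability by less than 0.1 point at 50% and 60%.

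**The case against.** The strongest reply is that the SAP does imply an order. Appendix 1 puts component LOCF first, SAP 6.3.2 mentions a missed visit, and Table RHCG.6.5 separates the response variable from its missing components. Missing response data could then mean the derived response, with NRI applied to whatever LOCF leaves unfilled. That reading is coherent, and because of it this is a matter of unstated precedence rather than flat contradiction. However, no text states it for a wholly missed visit, and SAP 6.3.4 points the other way by treating a missed visit as leaving JIA ACR30 missing.

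The second reply is rarity, and it stands. In the OLT period ixekizumab is given on site, and Visit 7 is a dosing visit with a window of ±7 days. Protocol Appendix 8 requires Visit 7 at site even in exceptional circumstances, widens the window to ±14 days and asks for missed procedures to be made up.

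A reader might go further than the documents allow in three ways:
- That SAP 6.3.4 settles the primary analysis as non-response. It sends COVID-19 misses to multiple imputation, which can yield a response, and it governs a sensitivity analysis only.
- That LOCF empties NRI of content or rescues dropouts. NRI still covers every pre-Week-16 treatment discontinuer and anyone with no post-baseline value.
- That Protocol 10.3.1.5.1 is silent. Its general rule leans towards non-response; it just does not name this case.

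**Conclusion.** The concern holds as an unresolved precedence between two rules for the primary endpoint, limited to ixekizumab participants still on treatment who miss all of Week 16 and have an earlier post-baseline visit. Followed literally, Appendix 1 departs from the estimand in SAP 4.1 for these participants.

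Exposure should be small. The number of such visits is an assumption throughout, because the documents give no rate, and the gaps in P(success) are conditional on the event occurring. With one missed visit they are 3 to 5 points at true rates of 50% to 60% when carried-forward response equals the true rate. One participant is enough to move the result across the line between 43 and 44 responders. A reader might infer that the stated false-positive rate is threatened; it is not, since at a true rate of 35% P(success) stays at or below 0.05% with one or two missed visits. The point should be fixed, but it does not undermine the design.

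**What to change.** In SAP 6.3.2 and Appendix 1 Scenario 2, state for the primary endpoint that:
- a Week 16 visit with all components missing is a non-response before any LOCF, in line with the composite estimand in SAP 4.1;
- component LOCF applies only to components missing at an attended Week 16 visit, with a stated limit on how many may be carried forward. The Scenario 3 limit (more than three missing gives non-response) is one option. Without a limit, one recorded component and five carried ones could still make a responder.

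Report the full-LOCF version as a sensitivity analysis. Use the same rule for the final and snapshot non-responder counts in SAP 6.15.1 and, where on-treatment participants with a missed visit are counted among the 40, for the interim rate in SAP 6.15. The interim is equally sensitive to one participant: 15/40 = 37.5% is futile and 16/40 = 40% is not.

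The cost is a few SAP sentences and a few lines of code. The primary response rate may be slightly lower. At a true rate of 60%, P(success) would be 81.5% with one missed visit and 77.8% with two, the latter below the stated 80%, against 84.8% under full LOCF with q = p. A cap on partial carry-forward could lower the rate a little further; the documents give no basis for sizing that.

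Separately, SAP 4.1 and 6.3.1 label Week 16 as Visit 8. The rest of the SAP uses Visit 7, and the label should be corrected as a clerical matter.

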6.1. Inclusion Criteria

Participants are eligible to be included in the study only if they meet all of the following criteria at enrollment:

Type of Participant and Disease Characteristics

- [1] Have a diagnosis with onset before the age of 16 years of any of the following categories of JIA as defined by the ILAR criteria (Petty et al. 2004):
 - ERA
 - JPsA
- [2] Have at least 3 active peripheral joints at screening and baseline. Active peripheral joint is defined as the presence of joint swelling or, in the absence of swelling, joint with limitation of motion plus pain on motion and/or tenderness on palpation.

Participant Characteristics

- [3] Participants with ERA must be from 6 to less than 18 years of age at screening and baseline.

Participants with JPsA must be from 2 to less than 18 years of age at screening and baseline.

Full date of birth will be collected except in countries in which it is not allowed.

- [4] Participants must weigh at least 10.0 kg.
- [5] Male or nonpregnant, non-breastfeeding female participants.

Participants of childbearing potential who are abstinent (if this is complete abstinence, as their preferred and usual lifestyle).

Total abstinence is defined as refraining from intercourse during the entirety of the study and for at least 12 weeks following the last dose of investigational product. Periodic abstinence such as calendar, ovulation, symptothermal, post ovulation methods, and withdrawal are not acceptable methods of contraception.

Otherwise, participants and their partners of childbearing potential must agree to use 2 effective methods of contraception, where at least 1 form is highly effective for the entirety of the study and for at least 12 weeks following the last dose of ixekizumab. Participants and their partners of childbearing potential must agree to use contraception for 5 months after the last dose of adalimumab.

The following contraception methods are considered acceptable (the participant, and their partner, should choose 2, and 1 must be highly effective [defined as less than 1% failure rate per year when used consistently and correctly]):

- Highly effective birth control methods:
 - Combined (estrogen- and progestogen containing) hormonal contraception associated with inhibition of ovulation: oral, intravaginal, or transdermal
 - Progestogen-only hormonal contraception associated with inhibition of ovulation: oral, intravaginal, or implantable

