9.1. Efficacy Assessments

9.1.1. Primary Efficacy Assessment

The primary efficacy endpoint is the percentage of ixekizumab treated participants meeting JIA ACR 30 response criteria at Week 16. A JIA ACR 30 response is defined as at least 30% improvement from baseline in 3 of any 6 variables in the core set, with no more than 1 of the remaining variables worsening by >30%.

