Appendix 1. Algorithm for Determining JIA ACRx Response

Details presented in this appendix will use “ x ” as a generic symbol, and the appropriate number (either 30, 50, 70, 90, or 100) is to be filled in when implementing in dataset programming code.

Juvenile idiopathic arthritis (JIA) American College of Rheumatology (ACR) x response is defined as at least $x\%$ improvement from baseline in at least 3 of any 6 variables in the core set, with no more than 1 of the remaining variables worsening by more than 30% from baseline.

- active joint count
- limited range of motion joint count
- physician global assessment of disease activity
- parent’s global assessment of well-being
- physical function as measured by Childhood Health Assessment Questionnaire (CHAQ), and
- erythrocyte sedimentation rate (ESR).

% change from baseline at a visit is calculated as:

$$(\text{value at visit} - \text{baseline value}) * 100 / \text{baseline value}$$

Change at a visit is calculated as:

$$\text{value at visit} - \text{baseline value}$$

The following abbreviations will be used throughout this appendix to refer to the items needed in the algorithm definitions:

Parameter	Abbreviation for the Parameter
% change from baseline in active joint count	AJ73
% change from baseline in limited range of motion joint count	LOM69
% change from baseline in parent’s global assessment of well-being	PGAWB
% change from baseline in physician’s global assessment of disease activity	PHYGA
% change from baseline in physical function as measured by Childhood Health Assessment Questionnaire (CHAQ)	CHAQ
% change from baseline in erythrocyte sedimentation rate (ESR)	ESR
Value of erythrocyte sedimentation rate	esr

Note:

- An *esr* value is within normal range if it is ≤ 20 .
- If the *esr* is elevated (*esr* > 20) due to JIA, then *esr* is used for calculation.
- If the *esr* is elevated due to a reason other than JIA, then *esr* is not used for calculation.
- If both baseline and postbaseline value of *esr* is within normal range (≤ 20), then the percent change of *esr* is set at 0 (no change).

JIA ACR30 Response Calculation

Two-step calculation; first step calculates worsening, and second step calculates improvement.

Step 1: Worsening (the increase in the score is worsening):

Check $> 30\%$ worsening. Specifically check if percent change from baseline is more than 30%, i.e.,

$$\text{If } (\text{parameter} > 30\%) = 1, \text{ else } 0$$

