- If either the Physician's Global Assessment of Disease Activity or the Parent's Global Assessment of Well-Being are used in the calculation of flare for a study visit, then a minimum worsening of at least 20 mm in 0 to 100 mm visual analogue scale (VAS) or 2 scores in the VAS of 21 circles from 0 to 10 must be present.

Flare Calculation

Calculation of flare (two-step calculation; the first step calculates improvement, and the second step calculates worsening).

Step 1: Improvement:

Check $\geq 30\%$ improvement. Specifically, check if percent change from baseline is less than or equal to -30% , i.e.,

$$\text{if } (\text{parameter} \leq -30\%) = 1, \text{else } 0$$

Count how many variables have not less than 30% improvement, if the improvement count is 2 or more, conclude that the patient is a non-flare patient. If the improvement count is 1 or less, proceed to Step 2.

Step 2: Worsening

Check $>30\%$ worsening. Specifically check if percent change from baseline is more than 30% , i.e.,

$$\text{Criteria 1: if } (\text{parameter} \geq 30\%) = 1, \text{else } 0$$

For variable: active joint count, limit of motion joint count, and Physician's Global Assessment of Disease Activity, also evaluate

$$\text{Criteria 2: if } (\text{variable at visit} - \text{variable at randomization} \geq 2) = 1, \text{else } 0$$

Note: if any of active joint count, limit of motion joint count, or physician assessment of disease activity has baseline value = 0, only Criteria 2 is required to determine the worsening, otherwise both Criteria 1 and 2 are required.

For variable: Parent's Global Assessment of Well-Being, also evaluate

*Criteria 3: if (variable at visit – variable at randomization $\geq 20\text{mm}$)
= 1, else 0*

Note: if Parent's Assessment of Patient Well-Being is with baseline value = 0, only Criteria 3 is required to determine the worsening, otherwise both Criteria 1 and 3 are required.

If baseline value of ESR is 0 and post-baseline value is nonmissing and out of normal range (i.e. ESR $>20\text{ mm/hr}$), consider it as worsening.

Count how many variables are worsening. If the worsening count is 3 or more, conclude as a flare patient, otherwise conclude as a non-flare patient.

Note:

Scenario 1: If no variable is missing, proceed as described in Step 1 and/or Step 2 whichever applies.

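### SAP Appendix 1 removes a core variable that is 0 at baseline from the worsening count as well as the improvement count, so the JIA ACR30 rule can err only toward response

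*SAP*

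**What the plan says.** Protocol 9.1.1 and SAP 6.9.1 define a JIA ACR30 response as improvement of at least 30% in three of the six core variables, "with no more than 1 of the remaining variables worsening by >30" per cent. Neither says what to do when a variable is 0 at baseline.

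SAP Appendix 1 turns this into two steps.
- Step 1 counts worsening by percent change alone: "Specifically check if percent change from baseline is more than 30" per cent, and "if the worsening count is 2 or more, conclude that the patient is a nonresponder".
- Step 2 counts improvement: "if the count is 3 or more, conclude that the patient is a responder".
- Scenario 3 covers zero baselines: "if there are variables with baseline value = 0, all postbaseline percent improvement is not calculable; hence, consider these variables as missing". The core set then shrinks. With two variables gone, the responder rule is "If 3 out of 4 components are improving and no more than 1 out of 4 is worsening"; with three gone, all three that remain must improve.

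The zero rule opens with a proviso allowing for exceptions, but Appendix 1 states none for a zero baseline. Its only special handling of values concerns ESR, chiefly that an ESR of 20 or less at both times is set to no change.

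SAP Appendix 2, the flare algorithm, has the same Scenario 3 clause but does state exceptions. If either joint count or the physician global "has baseline value = 0, only Criteria 2 is required to determine the worsening", meaning a rise of at least 2. A parent global of 0 has worsened if it rises by at least 20 mm, and an ESR of 0 has worsened if it rises above 20. CHAQ has no such rule.

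**The concern.** Treating a zero as missing merges two different situations. A missing baseline is unknown. A zero baseline is known, and the later value shows whether the child got worse. Dropping it is harmless for improvement, since a zero has no room to improve. For worsening it discards real information: a rise from no limited-motion joints to several is ignored, while a rise from one joint to several counts.

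The situation is open to eligible children. Inclusion criterion 2 in Protocol 6.1 requires at least three active joints, but "Active peripheral joint is defined as the presence of joint swelling or, in the absence of swelling", limited motion with pain or tenderness. Swelling alone therefore qualifies, and no minimum is set for limited-motion joints, parent global or CHAQ.

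The primary analysis compares one arm's response rate with a fixed 50%. A one-directional error in classifying response passes straight into that rate. The futility interim and the later nonresponder counts (SAP 6.15 and 6.15.1) use the same endpoint.

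**Working it through.** **1. The plan's own boundary.** Inputs: n = 80 on ixekizumab (SAP 5.2), prior Beta(0.5, 0.5) and success if P(p > 0.5 | k) is at least 0.80 (Protocol 10.3.3.1, SAP 6.9.1). The posterior is Beta(0.5 + k, 80.5 − k).
- k = 44: P(p > 0.5) = 0.814, success.
- k = 43: P(p > 0.5) = 0.749, failure.

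So 44 responders are needed, or at most 80 − 44 = 36 nonresponders. This reproduces the SAP 6.15.1 boundary of fewer than 37. The binomial tail P(K ≥ 44) is 84.8% at a true rate of 60% and 0.02% at 35%, consistent with the stated operating characteristics.

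**2. A child whose classification depends on the rule.**

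| Variable | Baseline | Week 16 | Appendix 1 | With Appendix 2 zero rules |
|---|---|---|---|---|
| Active joints | 6 | 3 | −50%, improved | improved |
| Limited-motion joints | 0 | 5 | dropped | rise 5 ≥ 2, worsened |
| Physician global | 6 | 3 | −50%, improved | improved |
| Parent global (mm) | 0 | 30 | dropped | rise 30 ≥ 20, worsened |
| CHAQ | 1.0 | 0.5 | −50%, improved | improved |
| ESR | 12 | 12 | no change | no change |

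Appendix 1 uses four variables, counts 3 improved and 0 worsened, and gives a responder. With the Appendix 2 zero-baseline rules the worsening count is 2, which Step 1 makes a nonresponder.

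**3. How sharp the edge is.** Change only the two zero baselines, to 1 joint and 5 mm. Percent changes become (5 − 1) × 100 / 1 = +400% and (30 − 5) × 100 / 5 = +500%. Appendix 1 as written now counts 2 worsened and gives a nonresponder.

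**4. One zero plus one ordinary worsening.** Parent global 0 to 30 mm and CHAQ 0.5 to 0.875 (0.375 / 0.5 = +75%), with active joints 6 to 3, limited-motion joints 4 to 2, physician global 6 to 3 and ESR 40 to 40. Appendix 1 uses five variables, 3 improved and 1 worsened: responder. Counting the parent global gives 2 worsened: nonresponder.

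**5. Direction.** Dropping a zero-baseline variable never removes an improvement. The rule that more than three missing variables means nonresponse gives no offset, because two or fewer variables cannot supply three improvements.

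**6. Size.** Each affected child adds 1/80 = 1.25 percentage points. The documents give no frequency of zero baselines; 0 to 3 of 80 (0 to 3.75 points) is an assumption. The probability of reaching 44/80, by rate under the repaired rule and by inflation from the present rule, is:

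| Repaired rate | +0 | +1.25 points | +2.5 points | +5 points |
|---|---|---|---|---|
| 50% | 21.7% | 28.8% | 36.9% | 54.6% |
| 60% | 84.8% | 89.6% | 93.2% | 97.5% |

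The top of the assumed range lies between the last two columns.

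**The case against.** The strongest reply is that Appendix 1 prespecifies a rule where the protocol is silent. SAP 6.1.2 and Appendix 1 define percent change by division by baseline, which is undefined at 0, so some convention is needed. That stands. A reader might infer that Appendix 1 contradicts the protocol definition; the documents do not support that. The point is that the chosen convention leans one way.

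A reader might also infer that any child with two newly worsened domains is scored a responder. That is too broad. At least three other variables must improve by 30% or more, and at most one of those remaining may worsen. Active joints cannot be 0 at entry. A physician global or ESR of exactly 0 seems unlikely (an assumption). The exposure is mainly limited-motion joints, parent global and CHAQ.

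Nor does the SAP already hold a complete substitute rule. If the two domains rising from zero are limited-motion joints and CHAQ, Appendix 2 counts only the first; the worsening count is 1 and the child remains a responder. Counting any CHAQ rise instead would be severe: with eight domains, one domain moving from 0 to 1 gives 1/8 = 0.125.

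The Appendix 2 thresholds were also written for flare, where they apply at non-zero baselines too. Borrowed only for zeros, they would pass 0 to 1 joint but count 1 to 2 joints (+100%). That is a fair cost.

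Two further replies carry less weight. A randomised adalimumab reference arm exists and gives context, but it does not enter the Bayesian test. Mean changes in all six components are summarised (SAP 6.9.2), so rises from zero contribute there, but that does not correct the response count.

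**Conclusion.** The concern holds in limited form. Appendix 1 discards known worsening from a zero baseline, the effect can only favour response, and the SAP treats the same variables differently in its flare algorithm without giving a reason. The size is unknown and probably small: 0 to 3 of 80 is assumed, at 1.25 points each. It alters the conclusion only if the result lies close to 44 of 80. At exactly 44, one reclassified child lowers the posterior from 0.814 to 0.749 and two lower it to 0.673. A reader might infer that the primary result is materially inflated; without the frequency of zero baselines the documents cannot show that. This is an inexpensive improvement to the primary derivation, not a reason to doubt the design.

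**What to change.** In Appendix 1 Scenario 3, keep a zero-baseline variable out of the improvement count but retain it in the Step 1 worsening count. Use the Appendix 2 zero-baseline rules: a rise of at least 2 for joint counts and physician global, at least 20 mm for parent global, and ESR above 20. For CHAQ, prespecify one justified threshold before the analysis, or leave CHAQ as now and report a sensitivity analysis. Do not count every rise above 0. Apply the same rule in both arms and to ACR50/70/90/100, and report how many children had each variable at 0 at baseline and how many change class.

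The cost is a few lines of SAP text and derivation code, with no new data. The reported response rate may be slightly lower, and the absolute thresholds will differ from the percent rule used when baseline is above 0.
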